## 6.8.4. Missing Start Date, Stop Date, Severity, or Relationship for Adverse Event

The same conventions to address incomplete dates for prior and concomitant medications will also be used for AEs. Should an event have a missing severity or relationship, it will be classified as having the highest severity and/or strongest relationship to study treatment.

### 6.8.5. Missing Time of First Dose or Time of Last Dose

In case of missing time for first dose, it will be assumed that baseline measures that were to be taken prior to first dose according to the protocol were in fact taken prior to dosing.

In case the time of the last dose is not reported, time of dose will be assigned as the median dosing time from all prior doses for the subject, as subjects are to dose once per day at approximately the same time each day.

## 6.8.6. Incomplete Date and Time for a Subject-Reported Attack

For HAE attacks reported with a missing stop date and or time, the following algorithm will be applied:

- Missing start time but start date present: The start time will be set to 12:00PM.
- Missing start date and time: The start date will be set to the date for which the question was answered "Yes". The start time will be set to 12:00PM
- Missing stop time, but stop date present: The stop time will be set to 11:59PM
- Missing stop date and time: The stop date will be set to the attack start date, the stop time will be set to 11:59PM

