#### Selection of duration that BCX7353 concentrations must exceed the target plasma level

To abate an attack, it is desirable to exceed the target plasma concentrations of BCX7353 as quickly as possible after a dose. HAE attacks typically follow a predictable time course. Swelling classically worsens slowly but relentlessly over the first 24 hours, and gradually subsides over the subsequent 48 to 72 hours. Following administration of a single dose formulated in a capsule in Study BCX7353-101, BCX7353 was rapidly absorbed. Mean plasma concentrations exceeded 71 ng/mL by 0.5 to 1 hour postdose at doses ranging from 250 to 1000 mg. Administration of a

liquid formulation in the current study is expected to achieve target levels earlier. In summary, target concentrations of BCX7353 are achievable early in the development of an HAE attack.

Current treatments for acute attacks of angioedema in HAE patients are administered parenterally, and sometimes retreatment is required after a period to time due to a lack of symptom relief. The label for Firazyr (icatibant) specifies that patients should administer additional doses every 6 hours if symptoms have not improved, and analysis of the open-label extension period of FAST-1 showed that 11.8% of treated attacks required more than one injection of Firazyr (icatibant) (Malbran, Riedl et al. 2014). The need for redosing could indicate that adequate plasma concentrations of icatibant are not of a sufficient duration to alleviate the symptoms of the attack or that a rebound effect is occurring. For an acute treatment, it would be advantageous to rapidly achieve plasma concentrations of BCX7353 at levels that lead to potent inhibition of plasma kallikrein, and maintain these concentrations above this level for longer than 6 hours.

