#### Subject-Reported Attack Rate

Diary entries for attacks are considered subject-reported attacks. The count of subject-reported attacks can differ from the count of confirmed attacks. In Parts 1 and 2, the investigator reviews each attack and either confirms it as an attack or rejects it as an attack. For Part 3, there is no investigator review of attacks, but an adjusted subject-reported attack rate will be computed based on a list of programmable requirements.

Subject-reported attack rates will be computed for Parts 1, 2, and 3.

#### Adjusted Subject-Reported Attack Rate for Part 3

Because there is no investigator-confirmation of attacks during Part 3, an adjusted subject-reported attack rate will be computed.

Subject-reported attacks must meet the following criteria (applied in order) for inclusion in the adjusted subject-reported rate computation:

- Attack must include at least 1 symptom of swelling
- Subject response to diary question, "In retrospect, could there be an alternative explanation for your symptoms other than an HAE attack (ie, allergic reaction, viral cold, etc)?" must be "no"
- Attack must be unique (attack begins > 24 hours from end of the prior attack), otherwise the event will be combined with and treated as a continuation of the preceding attack
- If untreated, attack must have a duration > 24 hours.

Adjusted subject-reported attack rates will be computed for the following reporting periods and expressed in units of attacks/month where 1 month = 28 days:

- Part 3, by month
- Part 3, entire dosing period

For adjusted subject-reported attack rates by month, months will be defined in blocks of 28 days, beginning on the first day of dosing in Part 3. If the subject discontinues treatment early, any attacks that occur within 24 hours after last dose will be counted in the calculation of subject-reported adjusted attack rate and the additional 24 hour-period will be included in the duration of the reporting period.

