### 6.8.3. Missing Start and Stop Dates for Prior and Concomitant Medication

For analysis of medications, a complete date should be established to identify medication as occurring during treatment or not. For the purposes of handling partially reported start and stop dates for medication the following algorithm will be applied:

• Missing start day, but month and year present:

If trial medication had been taken in the same month and year as the occurrence of the medication, then the start day of the medication will be assigned to the day of first dose of trial medication.

Otherwise the start day will be set to the first day of the month.

• Missing start day and month, but year present:

If trial medication had been taken in the same year as the occurrence of the medication, then the start date of the medication will be assigned to the date of first application of trial medication.

Otherwise the start day and month will be set to 01 January.

• Missing end day, but month and year present:

The day will be set to the last day of the month.

• Missing end day and month, but year present:

The end day and month will be set to the date of trial termination.

However, if trial termination year is greater than the year of the event/medication, then the day and month will be set to 31 December.

• For paper diaries where the date of an acute concomitant medication is missing, the date will be imputed as the date of the attack.

In subject data listings, start and stop date of medication will be displayed as reported on the eCRF.

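### An untreated Part 3 attack with neither stop date nor stop time recorded is imputed to last under 24 hours, so if it stands alone it always drops out of the adjusted attack rate

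*SAP*

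**What the plan says.** SAP 6.8.6 completes partial start and stop entries for attacks that subjects report, and it makes no exception for Part 3. The relevant line, for an attack with both stop date and stop time missing, is: "The stop date will be set to the attack start date, the stop time will be set to 11:59PM". Two neighbouring lines matter for comparison: "Missing start time but start date present: The start time will be set to 12:00PM" and "Missing stop time, but stop date present: The stop time will be set to 11:59PM". No line covers a recorded stop time with a missing stop date.

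Part 3 has no investigator confirmation, so SAP 6.7.5.1 replaces the confirmed rate with an adjusted subject-reported rate filtered by rule: "Subject-reported attacks must meet the following criteria (applied in order) for inclusion in the adjusted subject-reported rate computation". There are four criteria. The third merges an event with the preceding attack unless it starts more than 24 hours after that attack ended. The fourth and last is: "If untreated, attack must have a duration > 24 hours". SAP 6.7.5.5 measures a merged attack from the start of its first event to the end of its last. Nothing says how the fourth criterion treats an imputed stop.

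**The concern.** Each rule is workable alone. Together they decide the outcome in advance: the imputation always gives a duration that the filter rejects. Whether an untreated attack counts then depends on whether the subject wrote down when it ended, not on how long it lasted.

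Number and rate of attacks, and durability of response, are Part 3 secondary endpoints (SAP 3.2.9). The adjusted rate is the Part 3 counterpart of the confirmed rate and is plotted by month (SAP 8.6.1). Part 3 summaries of attack medication use are also built on adjusted attacks (SAP 8.7.4), so losing untreated attacks changes that denominator too. The 24-hour filter exists only in Part 3, so its deletions begin when the study moves from the e-diary to a paper diary without required confirmation (SAP 4.1). The missing-data sensitivity analyses in SAP 6.8.1, 6.8.2 and 8.6.2 concern Part 1, so none would reveal the effect.

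**Working it through.** The plan has no figure of its own to reproduce here. The inputs are the imputation lines in SAP 6.8.6, the ordered criteria in SAP 6.7.5.1 and the merged-duration rule in SAP 6.7.5.5.

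**1. Both stop fields missing.** Imputed duration = 23:59 on the start date minus the start time.
- Start 00:00: 23 h 59 min, the maximum.
- Start time missing, set to noon: 11 h 59 min.
- Start 23:59: 0 h.

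Of the 1,440 possible start minutes, 0 give more than 24 h.

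**2. Stop date recorded as the next day, only the time missing.** Imputed duration = 24 h + (23:59 minus start time). This exceeds 24 h for every start except 23:59, which gives exactly 24 h. So 1,439 of 1,440 pass. The same attack is nearly always kept if the subject writes the next day's date, and never kept if the stop is left blank and the attack stands alone.

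**3. Merging comes first, so some survive.**
- Attack A runs on day 1 from 08:00 to 20:00. B starts on day 2 at 10:00 with no stop, so it is imputed to end on day 2 at 23:59. The gap is 14 h, so they merge. Merged duration = day 1 08:00 to day 2 23:59 = 39 h 59 min, which is kept.
- A starts on day 1 at 15:00 with no stop, so it is imputed to end at 23:59. B runs from day 2 12:00 to day 3 06:00. The gap is 12 h 1 min, so they merge. Merged duration = 39 h, which is kept.

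The exclusion is therefore certain only for attacks that stand alone after the uniqueness rule.

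**4. The early end can also work the other way.** Take a 60 h attack starting on day 1 at 10:00. It truly ends on day 3 at 22:00, and another event starts 12 h later, on day 4 at 10:00. The true gap is 12 h, so the two count as one attack. With the stop missing, the imputed end is day 1 at 23:59 and the gap becomes 58 h 1 min, so they are separated. If the first was treated, it escapes the duration rule and two attacks can be counted instead of one. If it was untreated, it is separated and then deleted.

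**5. Size.** No document gives the share of Part 3 attacks with missing stops or the share left untreated. Let q be the share of otherwise countable attacks that are untreated, stand alone and lack both stop fields. Considering deletion only, adjusted rate after = adjusted rate before × (1 − q). Starting from 1.00 attacks/month, with q assumed:

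| q | adjusted rate |
|---|---|
| 2% | 0.98 |
| 5% | 0.95 |
| 10% | 0.90 |
| 20% | 0.80 |

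**The case against.** The strongest reply is that few attacks will be affected. Part 3 diaries are to be completed at least daily and are reviewed at visits, and the interim calls check that attack details are properly recorded (SAP Table 4 and its notes). Edit checks and data cleaning with sites also apply (SAP 6.3). Part 3 is open-label, its primary aim is safety, and its effectiveness analysis is descriptive, with no hypothesis test (SAP 8.1). All of this stands. It limits the likely size but does not remove the conflict: 6.8.6 exists because some stops will be missing, and each standalone untreated attack it handles in this way is lost.

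A reader might go further in several ways that the documents do not support.

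- **That every untreated attack with a missing stop is lost.** Merging is applied first, and the line requires both date and time to be missing.
- **That the trial's attack rate in general is distorted.** Only the Part 3 adjusted rate carries the 24-hour filter. The unadjusted subject-reported rate is also computed for Part 3, and the Part 1 primary endpoint uses investigator-confirmed attacks without that filter.
- **That long-term efficacy is necessarily flattered.** Each deletion lowers the rate, but splitting can raise it, and the balance is unknown.
- **That the imputation contradicts the sponsor's own description of attacks,** namely "Swelling classically worsens slowly but relentlessly over the first 24 hours, and gradually subsides over the subsequent 48 to 72 hours". That sentence is background in the protocol of the acute-treatment study BCX7353-202. The SAP is for the prophylaxis study BCX7353-302, where subjects take daily drug and treat attacks with standard of care. Neither document gives an attack duration for that setting.
- **That the SAP expects many incomplete attack stops on paper.** Its paper-diary line, "For paper diaries where the date of an acute concomitant medication is missing, the date will be imputed as the date of the attack", concerns medication dates only.

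**Conclusion.** The point holds in a narrow form. For an untreated Part 3 attack with both stop fields missing that stands alone after the uniqueness rule, the plan as written fixes the result: exclusion from the adjusted subject-reported rate, whatever the true length. This follows from the two rules and needs no assumption.

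Its effect on the reported rate does rest on an assumption. The loss equals q, which the documents do not give and which diary review should keep small. The direction of each deletion is certain, but the net direction of the imputation is not. This should be corrected because the rule gives a wrong answer for any such attack that truly exceeded 24 hours and the remedy is cheap. It does not threaten the primary analysis.

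**What to change.** In SAP 6.7.5.1, state that the 24-hour exclusion does not apply to a Part 3 attack with both stop date and stop time missing. Keep it where a stop date is recorded and only the time is missing. A recorded same-day stop shows that the attack did not last 24 hours, so exempting every imputed stop would count attacks that the rule is meant to exclude. Report the number of attacks affected, and present the adjusted rate with and without them.

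The alternative is to impute the missing stop as the start plus the subject's own median duration of complete attacks, capped at the next recorded attack. SAP 6.8.5 already fills a missing last-dose time with the subject's own median, so the approach has a precedent. It also eases the splitting problem, which the exemption alone leaves in place. Where the cap applies, the gap to the next attack is zero and the two would merge, so the text should say whether that is intended.

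Either change costs a few lines of SAP text and one derivation. The downside of the exemption is that some untreated attacks that truly lasted 24 hours or less may be counted, so the Part 3 adjusted rate may rise slightly. The summary with and without these attacks shows by how much.

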# 7. STUDY POPULATION

# 7.1. Subject Disposition

A summary table will be generated to provide the number and percentage (based on subjects randomized) of subjects in each of the analysis populations.

Subject status at the end of Part 1 will be listed and summarized as a Part 1 only display based on the ITT population, showing the number and percentage of subjects with early discontinuation of study treatment and early withdrawal from the study along with reasons for each item. Subjects

will be considered to have completed Part 1 if they have a Week 24 visit. A similar summary table and listing will be provided at the end of the study and will show discontinuations over the entire study period. The listings will include whether subjects discontinued from the study drug, whether they withdrew from the study and the reasons for the discontinuation of study drug, along with the date of first and last dose and the date of completion or discontinuation from the study drug and date of study withdrawal. Duration on study treatment and on the study will also be provided.

A CONSORT diagram will be created based on the summary tables for the CSR, starting with the number of subjects screened.

A summary of enrollment by country and investigator site will be provided.

## 7.2. Screen Failures

The number of screen failures and percent of screened subjects who are screen failures will be summarized along with reasons for screen failure. A summary and listing of demographic information for screen failures will be provided.

Confirmation of clinical diagnosis of HAE will be summarized based on the protocol inclusion criterion: C1 esterase inhibitor (C1-INH) functional levels, C4 levels, SERPING-1 gene mutation, and family history.

Additionally, SERPING result listings will show whether tested subjects were positive or negative for the SERPING-1 gene mutation and hence whether they failed screening due to a negative SERPING result.

# 7.3. Protocol Deviations and Listing of Subject Inclusion and Exclusion Criteria

Subjects who were randomized but did not satisfy all inclusion and exclusion criteria will be listed. A listing of subjects for whom the treatment blind was broken during the study will also be provided, if appropriate.

Protocol deviations will be included in listings and summaries for the CSR. A separate document will detail decision-making guidelines for determining whether a protocol deviation is major or minor and, for major protocol deviations, whether they would result in exclusion from the PP population. It will also detail a list of categories of protocol deviations. Protocol deviations will be reviewed in data review meetings prior to Part 1 unblinding to classify protocol deviations into categories, determine whether they are major or minor and to determine whether they will result in exclusion from the PP population.

Analyses based on the PP population will only be produced for Part 1 analysis.

A summary of all protocol deviations by type of deviation will be provided for Part 1.

A review of protocol deviations for Parts 2 and 3 will be conducted prior to database lock for the final CSR after the last subject has completed the last study visit. Protocol deviations for Parts 2 and 3 will be summarized by Part 2/3 treatment (Table 6) and category of deviation and will be listed but will not result in exclusion from the PP population.

# 7.4. Demographic and Baseline Characteristics

Demographic summary tables will be provided separately for Part 1 and the end of study (Table 6). The ITT and PP populations will be the primary populations for analyses of demographics. Demographics, including age, gender, race, ethnicity, childbearing potential, weight, height, and body mass index (BMI) will be listed and summarized. Age (in years) will be reported as the age at consent or assent, as collected in the eCRF.

BMI  $(kg/m^2)$  will be calculated using the standard formula:

BMI  $(kg/m^2) = Weight (kg)/[Height (m)]^2$ 

Confirmation of clinical diagnosis of HAE will be summarized based on the protocol inclusion criterion: C1-INH functional levels, C4 levels, SERPING-1 gene mutation, and family history. All SERPING results will be listed.

# 7.5. HAE Medical and Medication History

HAE and HAE medication history will be summarized for the following where possible:

- HAE history
- Past on-demand treatments of HAE
- Current on-demand treatments of HAE
- Past prophylactic treatments of HAE

Past on-demand treatments will include those medications that were taken as needed and discontinued prior to the initiation of study treatment as recorded on the HAE Medication History Page. Past prophylactic treatments will include those medications that were taken as prophylaxis and discontinued prior to the initiation of study treatment as recorded on the HAE Medication History Page. Current on-demand medications will include those that are noted at screening as currently used for on-demand treatment as recorded on the HAE Medication History Page. Summaries will include a grouping of any C1-INH medication as well as displays of individual medications. The C1-INH grouping will include plasma-derived C1-INH replacement (brand names = Cinryze, Berinert, HAEgarda), recombinant C1-INH replacement (brand name = Ruconest), icatibant (Brand name = Firazyr), Ecallentide (brand name = Kalbitor), fresh frozen plasma, and lanadelumab (brand name = Takhzyro). The summary of androgens will include androgens (unspecified), oxandrolone, danazol (brand name = Danocrine), and stanozolol.

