#### Criteria for inclusion:

- 1. Able to provide written, informed consent.
- 2. Males and non-pregnant, non-lactating females age 18 to 70 years.

- 3. A clinical diagnosis of hereditary angioedema Type 1 or Type 2, defined having a C1 INH functional level below 50% of normal and a C4 level below the lower limit of the normal reference range, as assessed at the Screening visit.
- 4. Access to and ability to use standard of care acute attack treatment. Standard of care acute attack treatment is defined as a medication approved by the relevant competent authority for the treatment of attacks of HAE (e.g. icatibant, ecallantide, plasma-derived C1INH, recombinant C1INH).
- 5. Female and male subjects must agree to the contraception requirements and must meet the inclusion criteria regarding contraception, and contraception of female partners (as applicable), as outlined in Section 8.2.
- 6. Any regularly administered concomitant medication recorded at the Screening visit and not stated as prohibited must be anticipated to be continued through the entire study and be of a stable dose and regimen for the duration of the entire study (screening through follow-up).
- 7. In the opinion of the Investigator, the subject is expected to adequately comply with all required study procedures for the duration of the study. To be dispensed study drug at baseline, the subject must demonstrate adequate compliance with all study procedures required from the Screening visit through randomization, including phoning the Investigator and diary recording of at least one HAE attack during the screening period.
- 8. Must have a documented HAE attack rate of at least 1 unique attack per month for 3 months (up to 93 days) within the 4 months prior to the Screening visit.

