As noted above, C1 INH is a covalent kallikrein inhibitor, and plasma-derived purified C1 INH (Cinryze®, Berinert®) and a human recombinant C1 INH (Ruconest®) are licensed for the treatment of acute HAE attacks in the European Union (EU). In the United States (US), Berinert® and Ruconest® are licensed for this indication. Kalbitor® (ecallantide) is an engineered recombinant protein noncovalent binding kallikrein inhibitor with homology to tissue factor pathway inhibitor and is licensed in the US for treatment of acute attacks of HAE by subcutaneous injection (Martello, Woytowish et al. 2012, Riedl 2012). In addition, Firazyr® (icatibant) is a bradykinin B2 receptor antagonist and is licensed in the EU and the US for treatment of acute attacks of HAE by subcutaneous injection.

The goal of acute treatment is to resolve angioedema symptoms as quickly as possible. There are no comparative (head-to-head) studies of therapies to treat an acute attack. Double-blind, randomized placebo-controlled trials have demonstrated superiority of Berinert, Cinryze Ruconest, Firazyr, and Kalbitor over placebo. These data are briefly described below.

Data from both the Berinert and the Cinryze trials suggest that higher doses (i.e., 20 U/kg Berinert, and more than 1 dose of Cinryze 1000 U) have a shorter median time to onset of relief with secondary outcomes consistently supported by the efficacy of the higher doses (Craig, Levy et al. 2009, Zuraw, Busse et al. 2010, Wasserman, Levy et al. 2011). With C1 INH, serious arterial and venous thromboembolic events have been reported at the recommended dose of C1 INH products. A general concern over transmission of blood-borne infections is inevitable when using human plasma—derived products. Hypersensitivity and allergic/pseudo-allergic systemic reactions have also been reported in a few patients. Berinert is approved in Europe for self-administration to treat all acute attacks and in the US to treat facial, laryngeal and abdominal attacks. Cinryze is approved in Europe to treat all acute attacks.

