Ruconest also demonstrated a treatment effect and the time to minimal symptoms was significantly shorter in patients receiving rhC1 INH compared to placebo with no subject in the rhC1 INH treatment group experiencing therapeutic failure (Zuraw, Cicardi et al. 2010). Hypersensitivity, including anaphylaxis in a single healthy volunteer with an undisclosed rabbit allergy, has been reported with the use of Ruconest. Ruconest is approved in Europe for treatment for all acute attacks and the US package insert has a limitation of use clause in the indication statement that states effectiveness was not established in HAE patients with laryngeal attacks.

Icatibant (Firazyr) is also an acute attack medication option for most patients in the US and EU. Icatibant is a subcutaneously-administered synthetic peptide that works distinctly from the other HAE treatments in that it functions as a bradykinin B2 receptor antagonist. In 3 published multicenter clinical trials (FAST 1, 2, and 3) patients were randomized to icatibant or comparator (placebo or tranexamic acid). Time to almost complete resolution was shorter with icatibant than with the comparator in all 3 trials and was statistically significant in the FAST 2 and FAST 3 trials (Cicardi, Levy et al. 2010, Lumry, Li et al. 2011). Open label studies have shown the benefit of different treatments for attacks at all sites. However, approximately 10% of patients require a second dose for re-emergent symptoms, usually 10 to 27 hours after the initial treatment (Longhurst 2010). Icatibant was generally well tolerated and is approved for the treatment of all HAE attacks.

Kalbitor (ecallantide) demonstrated a significantly higher improvement over placebo by using 2 measures of patient-reported outcomes and demonstrated efficacy at all attack locations (Riedl, Campion et al. 2010). The open-label extension phase of the studies suggested that the majority of patients benefited from a single dose of ecallantide, although in 29% of attacks a second dose was necessary due to incomplete efficacy (Levy, Lumry et al. 2010). Hypersensitivity (including anaphylaxis) is a known risk of ecallantide treatment for acute HAE attacks and is a black box warning label in the prescribing information, with a 4% incidence in treated patients. Ecallantide is approved for the treatment of all acute attacks of HAE.

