#### 17. **APPENDIX**

# **17.1.** Table of Contents for Data Display Specifications

Output #	Population	Output Title
14.1.1.1	ITT	Summary of Subject Disposition by Country and Site, Part 1
14.1.1.1.ES	ITT	Summary of Subject Disposition by Country and Site, Entire Study
14.1.2.1	ITT	Summary of Analysis Populations
14.1.2.2	ITT	Summary of Subgroups
14.1.2.3.1	ITT	Summary of Inclusion/Exclusion Criteria Deviations
14.1.2.3.2	Screen Failures	Summary of Inclusion/Exclusion Criteria Deviations
14.1.2.4	ITT	Summary of Protocol Deviations, Part 1
14.1.2.4.ES	ITT	Summary of Protocol Deviations that Occurred During Part 2
14.1.2.5	ITT	Summary of Confirmation of Diagnosis of HAE Type I or II
14.1.3.1.1	ITT	Summary of Demographic Characteristics
14.1.3.1.1.ES	ITT	Summary of Demographic Characteristics - Subjects Who Transitioned to Part 2
14.1.3.1.2	РР	Summary of Demographic Characteristics
14.1.3.1.3	Screen Failures	Summary of Demographic Characteristics
14.1.3.2	ITT	Summary of Subject-Reported HAE Baseline Characteristics - HAE Medical History
14.1.3.3	ITT	Summary of Past Prophylactic Treatments of HAE
14.1.3.4	ITT	Summary of Current On-Demand Treatments of HAE
14.1.3.5	ITT	Summary of Subject-Reported HAE Baseline Characteristics – Primary Acute Attack Treatment Information
14.1.3.6	ITT	Summary of Pre-Treatment Investigator-Confirmed Attack Rates and Angioedema Symptoms
14.1.4.1	ITT	Summary of Medications Taken within 30 Days of Screening and Discontinued Prior to Dosing
14.1.4.2	ITT	Summary of Concomitant Medications, Part 1
14.1.4.2.ES	ITT	Summary of Concomitant Medications – Entire Study
14.1.4.3	ITT	Summary of Concomitant Medications for HAE, Part 1
14.1.4.3.ES	ITT	Summary of Concomitant Medications for HAE, Entire Study
14.1.4.3.P3	ITT	Summary of Concomitant Medications for HAE, Part 3
14.1.4.4	ITT	Summary of Concomitant Medications for HAE – Attack Level, Part 1
14.1.4.4.ES	ITT	Summary of Concomitant Medications for HAE – Attack Level, Entire Study
14.1.4.4.P3	ITT	Summary of Concomitant Medications for HAE – Attack Level, Part 3
14.1.5.1	Safety	Summary of Treatment Exposure and Treatment Compliance, Part 1
14.1.5.1.ES	Safety	Summary of Treatment Exposure and Treatment Compliance, Entire Study
14.2.1.1	ITT	Summary of Hierarchical Testing for Efficacy Endpoints
14.2.1.2.1	ITT	Overall Attack Summary During Part 1
14.2.1.2.1.ES	ITT	Overall Attack Summary During Entire Study
14.2.1.2.2	РР	Overall Attack Summary During Part 1

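### SAP 7.5 counts icatibant and ecallantide as C1-INH medications, so the grouped row can exceed true C1-INH use

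*SAP*

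**What the plan says.** SAP 7.5 covers HAE medical and medication history: past and current on-demand treatment and past prophylaxis. It says: "Summaries will include a grouping of any C1-INH medication as well as displays of individual medications". It then lists what the C1-INH grouping contains. The list starts with the plasma-derived products (Cinryze, Berinert, HAEgarda) and continues "recombinant C1-INH replacement (brand name = Ruconest), icatibant (Brand name = Firazyr), Ecallentide (brand name = Kalbitor), fresh frozen" "plasma, and lanadelumab (brand name = Takhzyro"). That makes eight entries. The summary of androgens is defined separately.

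Among the displays in SAP 17.1, the row would appear in Table 14.1.3.4, "Summary of Current On-Demand Treatments of HAE", in the ITT population.

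Protocol 5.1 says of Firazyr that "icatibant) is a bradykinin B2 receptor antagonist and is licensed in the EU and the US", and that it "works distinctly from the other HAE treatments in that it functions as a bradykinin B2 receptor antagonist". It says of Kalbitor that "ecallantide) is an engineered recombinant protein noncovalent binding kallikrein inhibitor with homology to tissue factor pathway inhibitor". The inclusion criterion on standard-of-care attack treatment gives four separate examples: "e.g. icatibant, ecallantide, plasma-derived C1INH, recombinant C1INH".

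**The concern.** The row's label and its contents disagree. A reader will take the any-C1-INH row as the share of subjects with C1 esterase inhibitor treatment in their history. As defined, it also counts subjects who have used only a bradykinin B2 receptor antagonist or an engineered kallikrein inhibitor. This is a stated derivation rule and leaves the programmer no discretion, so the wrong count would carry through to the clinical study report.

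What is at stake is the description of background treatment. The row exists to say how many subjects in each arm have been treated with C1-INH, and with these members it cannot say that.

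**Working it through.** The plan states no figure for this row, so there is nothing to reproduce. The check sets the eight entries against what the documents say about each.

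| Entry in the SAP 7.5 grouping | What the documents say | C1-INH product? |
|---|---|---|
| Cinryze, Berinert, HAEgarda | SAP 7.5: plasma-derived C1-INH replacement | Yes |
| Ruconest | SAP 7.5: recombinant C1-INH replacement | Yes |
| Icatibant | Protocol 5.1: bradykinin B2 receptor antagonist; listed apart from C1-INH in the inclusion criteria | No |
| Ecallantide | Protocol 5.1: engineered kallikrein inhibitor; listed apart from C1-INH in the inclusion criteria | No |
| Fresh frozen plasma | Protocol 7.1.2: same washout branch as plasma-derived C1-INH | Open |
| Lanadelumab | Not described beyond its place in this list | Open |

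So 4 of the 8 entries are C1-INH by the SAP's own wording, 2 belong to other classes by the protocol's wording, and 2 need a decision.

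**Direction.** In one treatment group, let
- T = subjects with at least one of Cinryze, Berinert, HAEgarda or Ruconest;
- F = subjects with none of those four but with fresh frozen plasma or lanadelumab;
- E = subjects whose only listed drugs are icatibant and/or ecallantide.

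The row as defined is R = T + F + E. With icatibant and ecallantide removed, and fresh frozen plasma and lanadelumab left in for now, it is R' = T + F. The difference is R − R' = E, which cannot be negative. The row therefore equals or exceeds true C1-INH use however the two open entries are settled.

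**Size per subject.** The SAP summary plans 40 per group and about 120 in total.
- In one group: 1/40 = 2.5 percentage points.
- Overall: 1/120 = 0.8 percentage points.

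**Size in total.** The excess is s = E/40. The documents give no value for s, so these are assumptions only:
- s = 10%: 4 of 40, 10 points too high.
- s = 25%: 10 of 40, 25 points too high.
- s = 50%: 20 of 40, 50 points too high.

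If no subject falls in E, the excess is zero.

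**Can the individual rows repair it?** Not fully. If two C1-INH products have a and b users, the number using at least one lies anywhere between the larger of a and b and the sum a + b, because a subject may have used both. Per-drug counts alone do not give the de-duplicated total T.

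**Which displays.** Protocol 5.1 describes icatibant and ecallantide as treatments for acute attacks, so the effect falls mainly on current on-demand treatment (Table 14.1.3.4). SAP 7.5 also plans a past on-demand summary where possible. SAP 17.1 lists no table for it, only Listing 16.2.4.3.3. The past table that is listed, 14.1.3.3, covers prophylaxis.

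**The case against.** The strongest reply is that nothing inferential depends on this row. It enters no model, subgroup or hypothesis in SAP Section 8, and prior C1-INH exposure is not among the items SAP 8.2 names for baseline comparability. The same SAP sentence requires individual drugs to be shown, so use of each C1-INH product stays visible by arm. This stands, and it limits the point to one descriptive line. It does not make that line correct.

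The protocol supplied is for Study 202 and the SAP is for Study 302, and the protocol never says outright that these two drugs are not C1-INH. It assigns them to other classes. That is also true, but a drug's class does not change between studies, and SAP 7.5 itself attaches the term C1-INH replacement only to the plasma-derived and recombinant products.

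Table shells are held in a separate document, and SAP 6.4 allows minor title changes without a SAP revision, so the label might be corrected there. Nothing supplied shows this. Membership of the group is data handling rather than format.

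Several stronger readings are tempting, and the documents do not support them:
- A reader might infer that lanadelumab is also misplaced and that past C1-INH prophylaxis is overstated. No supplied document gives lanadelumab's mechanism; the only text that places it is this list.
- A reader might infer that fresh frozen plasma is misplaced. The protocol's attack-interval rule puts plasma preparations with plasma-derived C1-INH. That rule also puts icatibant with recombinant C1-INH, so it sorts by interval and not by class, and it settles neither question.
- A reader might infer that the row hides an imbalance between arms. One can construct a case: with C1-INH use of 30% and 50%, icatibant use of 80% in both arms and independence, the row reads 1 − 0.7 × 0.2 = 86% against 1 − 0.5 × 0.2 = 90%. Every input is assumed, and the per-drug rows by arm would still show the individual C1-INH products.

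**Conclusion.** The point holds for icatibant and ecallantide. The grouping as defined counts users of only those drugs as C1-INH users, so the row can equal or exceed true C1-INH use and can never fall below it. Each such subject adds 2.5 points in a group of 40. The total is unknown and depends on how many subjects used icatibant or ecallantide and nothing else on the list.

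The conclusion rests on two things: the drug classes in the Study 202 protocol carry over to Study 302, and the row is programmed as SAP 7.5 states. It is a minor descriptive error with no bearing on efficacy or on the testing strategy. It is still worth correcting, because the reported figure would not mean what its label says.

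**What to change.** In SAP 7.5:
- Keep Cinryze, Berinert, HAEgarda and Ruconest in the C1-INH grouping.
- Remove icatibant and ecallantide and show each as its own row.
- Have the sponsor confirm and state where fresh frozen plasma and lanadelumab belong.

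If the broad row is also wanted, keep it beside a true C1-INH row under its own label, for example *any non-androgen HAE medication listed*. It should not be called targeted medication. SAP 6.7.5.7 already uses that term for a different list, one that includes androgens and names neither HAEgarda nor lanadelumab.

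The cost is a sentence of SAP text and one grouping variable, plus one further row if the broad grouping is kept. No data collection changes.
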